4.1.2 Dosing Delay Criteria

Prior to every AGEN1884 administration, laboratory values will be reviewed. AGEN1884 administration will be delayed for the following adverse events (AEs), if the following AEs occur on the day of planned AGEN1884 dosing:

- Either febrile neutropenia or neutropenia <500 cells/mm³ for >1 week despite the use of growth factors.
- Any grade ≥2, non-skin, drug-related AE except for fatigue and laboratory abnormalities
- Any grade 3 drug-related laboratory abnormality (except lymphopenia, AST, ALT, total bilirubin, or asymptomatic lipase or amylase).
 - o Grade 3 lymphopenia does not require a dose delay.
 - o If the subject has a baseline AST, ALT, or total bilirubin that is within normal limits, dosing should be delayed for drug-related grade ≥2 toxicity.
 - o If the subject has a baseline AST, ALT, or total bilirubin within the grade 1 toxicity range, dosing should be delayed for drug-related grade ≥3 toxicity.
 - o Any grade 3 drug-related amylase or lipase abnormality that is not associated with symptoms or clinical manifestations of pancreatitis does not require dose delay.
- Any grade 3, skin, drug-related AE.
- Any AE, laboratory abnormality, or intercurrent illness that, in the judgment of the investigator, warrants delaying the dose of study medication.
- For subjects in Phase 2 with HCC and an elevated baseline liver function test:

Dose delay for the following:

- Baseline AST, ALT \leq 2 x ULN with an increase to \geq 5 x ULN
- Baseline AST, ALT ≥ 2 x ULN with an increase to ≥ 3 x the baseline level
- Elevations of AST, ALT ≥500 IU/L or 20 x ULN regardless of baseline level
- Baseline total bilirubin ≤ 1.5 x ULN and increase to ≥ 2 x ULN
- Baseline total bilirubin >1.5 x ULN and increase to \geq 2 x baseline level
- Elevations of total bilirubin $\ge 3x$ ULN regardless of baseline level

Permanently discontinue for

- Elevations of ALT ≥20 x ULN regardless of baseline level
- Clinical Hepatic Decompensation regardless of lab values as follows:
 - New onset clinical ascites
 - Upper gastrointestinal bleeding due to portal hypertension
 - o Encephalopathy
 - Coagulopathy due to liver disease
 - Worsening Child-Pugh score to 9

Confidential Page 34 of 78

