4.4.2 Permanent Treatment Discontinuation

The following ADRs require permanent treatment discontinuation of AGEN1884:

Any grade 4 ADRs except for single laboratory values out of normal range that are unlikely related to trial treatment as assessed by the investigator, do not have any clinical correlate, and resolve within 7 days with adequate medical management.

Any grade 3 ADRs except for any of the following:

- Transient (≤6 hours) grade 3 flu-like symptoms or fever, which are controlled with medical management.
- Transient (≤24 hours) grade 3 fatigue, local reactions, headache, nausea, or emesis that resolves to grade ≤1.
- Single laboratory values out of normal range (excluding grade ≤3 liver function test increase) that are unlikely related to trial treatment according to the investigator; do not have any clinical correlate; and resolve to grade ≤1 within 7 days with adequate medical management.
- Tumor flare phenomenon, defined as local pain, irritation, or rash localized at sites of known or suspected tumor.
- Any grade ≥3 drug-related amylase or lipase abnormality that is not associated with symptoms, or clinical manifestations of pancreatitis does not require dose delay. The trial medical monitor should be consulted for such grade ≥3 amylase or lipase abnormalities.
- Increases in ECOG performance status to ≥3 that do not resolve to ≤2 by Day 14 of the following cycle (infusions should not be given on the following cycle if ECOG performance status is ≥3 on day of study drug administration).

Any grade 2 ADR should be managed as follows:

- If a grade 2 ADR resolves to grade ≤1 by the last day of the current cycle, trial treatment may continue.
- If a grade 2 ADR does not resolve to grade ≤1 by the last day of the current cycle, infusions should not be administered during the following cycle. If, at the end of the following cycle, the event has not resolved to grade 1, the subject should permanently discontinue treatment with AGEN1884.
- For grade 2 ADRs related to hormone insufficiencies that can be managed by replacement therapy, up to 2 subsequent doses may be omitted.
- Upon the second occurrence of the same grade 2 ADR (except for hormone insufficiencies that can be managed by replacement therapy) in the same subject, treatment with AGEN1884 should be permanently discontinued.

Confidential Page 46 of 78

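### Section 4.4.2 gives two incompatible instructions for a grade 4, drug-related, asymptomatic amylase or lipase rise

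*Protocol*

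**What the plan says.** Protocol Section 4.4.2 opens with "The following ADRs require permanent treatment discontinuation of AGEN1884" and then sets separate rules by grade.

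- **Grade 4 rule:** "Any grade 4 ADRs except for single laboratory values out of normal range that are unlikely related to trial treatment". To qualify for this exception, the value must also have no clinical correlate and resolve within 7 days.
- **Grade 3 rule:** "Any grade 3 ADRs except for any of the following", followed by a bulleted list. One bullet begins "Any grade ≥3 drug-related amylase or lipase abnormality that is not associated with symptoms", extends the condition to clinical signs of pancreatitis, and states that such a value needs no delay in dosing. The next sentence adds: "The trial medical monitor should be consulted for such grade ≥3 amylase or lipase abnormalities".

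Protocol Section 4.1.2, on dose delay, has almost the same sentence with a different grade: "Any grade 3 drug-related amylase or lipase abnormality that is not associated with symptoms or clinical manifestations of pancreatitis does not require dose delay". The laboratory criterion above it is also written for grade 3. The separate criterion for non-skin events of grade 2 or higher leaves out laboratory abnormalities.

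Table 12 (Section 5.8.4), which lists the laboratory tests, includes neither amylase nor lipase.

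**The concern.** The grade 4 rule and the amylase/lipase bullet stand in the same section and both reach a grade 4 value that is related to the drug and causes no symptoms. One makes the stop mandatory. The other lists the value as an exception to stopping, says dosing need not be delayed, and sends the case to the medical monitor. The bullet also answers a different question from its list: the list concerns permanent discontinuation, while the bullet speaks of delay. An investigator cannot tell whether it lifts the stop, the delay, or both.

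Safety and tolerability are a primary objective. Protocol Section 6.4.1 and SAP Section 8.6.2 plan summaries of discontinuations due to adverse events, and SAP Section 8.6.1 plans summaries of exposure and dose intensity. If two sites follow different sentences for the same finding, part of the difference in those summaries comes from the wording of the protocol and not from the drug.

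**Working it through.** The plan states no figure to reproduce on this point. The check takes one event, an amylase or lipase rise that is drug-related and asymptomatic, and asks what each rule says at grade 3 and at grade 4.

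**Step 1: can a drug-related value use the grade 4 exception?** No. The exception requires the value to be unlikely related. On the causality scale in Protocol Section 5.9, unlikely is a separate category from possible, probable and definite. SAP Section 8.6.2 counts only the last three as related. A value cannot be both drug-related and unlikely related, so the grade 4 rule gives a permanent stop.

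**Step 2: set the rules side by side.**

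| Rule | Grade 3 | Grade 4 |
|---|---|---|
| 4.4.2, grade 4 rule | Does not apply | Permanent stop |
| 4.4.2, amylase/lipase bullet | Exempt from the stop; no delay required; consult the medical monitor | Same, because the stated range is grade 3 and above |
| 4.1.2, laboratory delay criterion and its exemption | No delay required | Not addressed |

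At grade 3 the two sections agree on dosing. The conflict is confined to grade 4 and lies between the first two rows.

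**Step 3: does Section 4.1.2 add a third answer?** No. Its laboratory trigger and its exemption both name grade 3, and its grade 2 or higher trigger excludes laboratory abnormalities. At grade 4 it orders no delay, so no exemption is needed. Only its general clause on investigator judgment remains. It differs from the Section 4.4.2 bullet in grade range without contradicting either instruction.

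**Step 4: what would one case do to the summaries?** The documents give no rate for such events, so the number of cases cannot be estimated. The weight of a single case follows from the planned Phase 2 numbers (up to 60 subjects, about 20 of them with hepatocellular carcinoma, HCC). It assumes those targets are met and that the subject has no other event leading to discontinuation:

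- All of Phase 2: 1/60 = 1.7 percentage points on the proportion who discontinue due to an adverse event.
- HCC subgroup: 1/20 = 5 percentage points.

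Exposure moves too. Under SAP Section 8.6.1, a subject withdrawn before Cycle 4 for a reason other than progression or death has the remaining cycles counted at 3 weeks and zero dose. For example, a subject stopped after two full doses, with no delays, would have 2 doses over 4 × 3 = 12 weeks. A subject who continued would have 4 doses over the same 12 weeks, so the first figure is 2/4 = 50% of the second.

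**The case against.** The strongest reply is that Section 4.4.2 has two separate rules, each with its own exceptions. A bullet under the grade 3 rule does not naturally override the grade 4 rule, and this bullet speaks only of delay. On that reading the grade 4 stop is intact and the range is loose drafting. The reading is possible, but it does not remove the problem. The range of grade 3 and above is written twice, once in the bullet and once in the sentence on consultation, and would have no effect at grade 4. A value that requires a permanent stop would also be described as not requiring a delay. The other bullets that name the grade of the exempted event name grade 3, so the wider range looks like a real difference.

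Section 5.8.6.4 might be thought to settle the matter, since it lets grade 3 or 4 events be considered for discontinuation after consulting the medical monitor. That wording is discretionary and does not say which mandatory sentence of Section 4.4.2 governs.

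Three further points stand and limit the concern:

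- The exempt branch is not an absence of action. A reader might infer that the bullet lets dosing continue with nothing done, but it calls for the medical monitor, who could notice and even out differences between sites.
- Cases may be rare. The value must be grade 4, related and symptom-free, and must come from a test that the protocol does not schedule.
- An abnormal laboratory value is an adverse event only if judged clinically significant (Sections 5.8.6.1.1 and 5.8.6.2.1), so some asymptomatic values may never be classed as ADRs.

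**Conclusion.** The inconsistency is real and sits inside Section 4.4.2. For a grade 4, drug-related, asymptomatic amylase or lipase rise, the grade 4 rule and the amylase/lipase bullet cannot both be followed as written. Section 4.1.2 adds a mismatch in grade range only.

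Two stronger readings are not supported. A reader might infer three conflicting instructions, but Section 4.1.2 is silent at grade 4. A reader might also infer that exposure and the discontinuation tables will be distorted. The documents show only that they could be: they give no event rate, and neither test is in Table 12. The effect is possible and probably small in number, although one case would weigh about 1.7 points in 60 subjects or 5 points in 20.

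The conclusion assumes that the range in the bullet means what it says and that the value has been classed as an ADR. It takes no position on which clinical rule is right. The point is worth correcting because it concerns a mandatory stopping rule in a trial whose primary objective is safety.

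**What to change.** The sponsor should reconcile the grade 4 rule and the amylase/lipase bullet in Section 4.4.2, then align the matching sentence in Section 4.1.2. After the change, all three places should:

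- name the same grade range for asymptomatic amylase or lipase values;
- state one consequence for each grade, and say whether it concerns delay or discontinuation;
- say where consultation with the medical monitor fits.

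Which grade range and which consequence apply is for the sponsor to decide.

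The cost is a few sentences in a protocol amendment, plus the written IRB/IEC approval that Section 7.1 requires before a change takes effect. It could be combined with another amendment. No sample size, endpoint or analysis method changes. If cases have already occurred, the study report should list each one with the action taken, so that readers can see which sentence was followed.

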3.1.2.2 Definition of Dose-Limiting Toxicity

With exceptions discussed below, a DLT is defined as a grade ≥3 adverse drug reaction (ADR), according to the National Cancer Institute (NCI) Common Terminology Criteria for Adverse Events (CTCAE) Version 5, occurring in the DLT evaluation period (i.e., 28 days after the initial administration of AGEN1884) in subjects enrolled in the phase 1 dose escalation.

The SRC recognizes that in the absence of prior human experience with AGEN1884, a conservative approach should be adopted in ascribing the relevance of the treatment-related toxicity to drug. Treatment-emergent serious adverse events (SAEs) will be ascribed as related to drug except in cases in which a clear relationship to the underlying disease or recognized comorbidities are evident. For this trial, the MTD is defined as the highest dose at which <2 of 6 subjects experience a DLT.

A DLT is specifically defined as any one of the following:

- Grade ≥ 2 uveitis, eye pain, or blurred vision that does not respond to topical therapy.
- Any grade ≥3 toxicity that is possibly, probably, or definitely related to AGEN1884
 occurring during the DLT evaluation period (28 days after initial administration of
 AGEN1884), except for any of the following:
 - Grade 3 infusion-related reaction resolving within 6 hours of dosing and controlled with medical management.
 - Transient (≤6 hours) grade 3 flu-like symptoms or fever, which are controlled with medical management.
 - Transient (≤24 hours) grade 3 fatigue, local reactions, headache, nausea, or emesis that resolves to grade ≤1.
 - Grade 3 diarrhea, skin toxicity, or liver function test (LFT), (alanine aminotransferase [ALT], aspartate aminotransferase [AST], or gamma glutamyltransferase [GGT]) increase that resolves to grade ≤1 within 7 days after medical management (e.g., immunosuppressant treatment) has been initiated.
 - Single laboratory values out of normal range that are unlikely related to trial treatment according to the investigator, do not have any clinical correlate, and resolve to grade ≤1 within 7 days with adequate medical management.
 - Tumor flare phenomenon, defined as local pain, irritation, or rash localized at sites of known or suspected tumor.

Subjects who do not complete the DLT observation period and do not receive 2 doses of AGEN1884 during the DLT observation period for reasons other than a DLT will be replaced.

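### Section 4.4.2 lists unresolved drug-related ECOG declines to 3 or more as an exception to permanent discontinuation, so the literal rule runs backwards

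*Protocol*

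**What the plan says.** Protocol Section 4.4.2 sets out which adverse drug reactions (ADRs) end treatment for good. Its grade 3 rule is introduced by "Any grade 3 ADRs except for any of the following" and is followed by six bullets. The sixth reads "Increases in ECOG performance status to ≥3 that do not resolve to ≤2 by Day 14 of the following cycle", with a bracketed instruction that "infusions should not be given on the following cycle if ECOG performance status is ≥3 on day of study drug administration".

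Other rules in the same section, and the parallel list in Section 3.1.2.2, treat resolution as follows:

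- Another grade 3 exception in 4.4.2: "Transient (≤24 hours) grade 3 fatigue, local reactions, headache, nausea, or emesis that resolves to grade ≤1".
- The grade 4 exception in 4.4.2 covers isolated laboratory values that are unlikely to be related to treatment, provided they "do not have any clinical correlate, and resolve within 7 days with adequate medical management".
- The grade 2 rule in 4.4.2, after one cycle of withheld infusions: "If, at the end of the following cycle, the event has not resolved to grade 1, the subject should permanently discontinue treatment with AGEN1884".
- Two exceptions to the dose-limiting toxicity (DLT) definition in 3.1.2.2: "Grade 3 infusion-related reaction resolving within 6 hours of dosing and controlled with medical management", and a grade 3 diarrhea, skin or liver-test "increase that resolves to grade ≤1 within 7 days after medical management (e.g., immunosuppressant treatment) has been initiated".

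**The concern.** An exception to a stopping rule normally lets off the event that goes away. Here the event that does not go away is let off. A drug-related fall to ECOG 3 or worse that persists past the deadline is exempt from the mandatory permanent stop. The same fall, recovered in time, is outside the exemption and ends treatment if it counts as a grade 3 ADR. The section then treats an unresolved grade 2 reaction more strictly than an unresolved fall to ECOG 3.

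At stake is a mandatory safety rule that sites could apply in opposite ways: some following the literal text, others what they take to be its intent. Tolerability is part of the primary endpoint, and discontinuations due to adverse events are reported (Protocol 6.4.1, SAP 8.6.2).

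**Working it through.** The plan states no figure to reproduce. The check compares rules and counts wording.

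**1. Direction of the resolution conditions.** Only exceptions that say explicitly whether the event resolves are counted in the last three columns.

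| Place | Exceptions | With a resolution condition | Exempt if resolved | Exempt if not resolved |
|---|---|---|---|---|
| 4.4.2, grade 3 list | 6 | 3 (fatigue group, single laboratory values, ECOG) | 2 | 1 (ECOG) |
| 4.4.2, grade 4 rule | 1 | 1 (single laboratory values) | 1 | 0 |
| 3.1.2.2, DLT list | 6 | 4 (infusion reaction, fatigue group, diarrhea/skin/liver tests, single laboratory values) | 4 | 0 |

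Totals: 3 + 1 + 4 = 8 with a resolution condition; 2 + 1 + 4 = 7 exempt the resolved event; 1 exempts the unresolved event. Within Section 4.4.2 alone the split is 3 to 1. The DLT list has no ECOG item.

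**2. Outcome for a decline to ECOG 3 or more that counts as a grade 3 ADR, with no other stopping reaction.**

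| State by Day 14 of the following cycle | As written | After correction |
|---|---|---|
| Back to 2 or less | Not exempt: permanent stop | No stop on this ground |
| Still 3 or more | Exempt: infusions held only | Permanent stop |

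**3. Does another section repair it?** None does.

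- Section 3.5 offers unacceptable toxicity, an adverse event or investigator decision as grounds, with no ECOG threshold.
- Section 3.7 considers ECOG decline only for treatment beyond progression.
- Section 4.1.2 has no ECOG criterion for delaying a dose, only a general judgement clause.
- The HCC stops at the end of Section 4.4.2 have no ECOG item.
- Section 5.8.6.4 says only that grade 3 or 4 events may lead to discontinuation.

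**4. Who is affected?** ECOG is not a CTCAE grade, so the bullet applies only where the decline is treated as a grade 3 ADR. That is plausible: where CTCAE does not apply, Section 5.8.6.4 grades an event as severe if normal daily activities become impossible, and Appendix C describes ECOG 3 as limited self-care with more than half of working hours in bed or a chair.

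The subject must also have no concurrent reaction that already forces a stop. Those include:

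- another non-exempt grade 3 ADR, such as grade 3 fatigue beyond 24 hours, or a non-exempt grade 4 ADR;
- a grade 2 ADR that persists or recurs (hormone insufficiencies apart);
- grade 3-4 gastrointestinal, pulmonary, hepatic or neurological immune-related events (Tables 4, 5, 6 and 9; HCC subjects have separate hepatic rules);
- the Hy's Law stop in Table 6, or a grade 2 infusion reaction despite premedication (Table 2).

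Example: a subject is at ECOG 3 on Day 14 of the following cycle and at ECOG 1 at the next dosing visit, with none of the above. The literal text allows re-dosing; the corrected text does not.

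**5. Can the deadline be observed?** Table 10 places ECOG at screening, on Day 1 of Cycles 1 to 4, at the visits after Week 12, and at the end-of-treatment and final safety visits. The mid-cycle visits (Cycle 1 Day 8, Cycle 4 Day 15) have none, and no Day 14 assessment is scheduled. In a 3-week cycle the next Day 1 is Day 22, which is 22 − 14 = 8 days after the deadline. After Week 12, if a cycle is taken to equal the dosing interval (an assumption), the gap is 43 − 14 = 29 days on the 6-week schedule and 85 − 14 = 71 days on the 12-week schedule.

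**The case against.** **The list level may be an artefact.** The bullet would read naturally as a stop of its own, beside the grade 3 and grade 4 rules. If the source page sets it at that level, nothing is wrong. Marker levels are uneven elsewhere in the extracted text, for example under hepatic decompensation in Section 4.1.2. This stands as a dependency. Against it, all six bullets carry the same marker, and nested levels survive in Section 3.1.2.2.

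**A reversed condition is not proven.** A reader might infer that the word *not* was inserted by mistake. The documents do not establish this. A stop criterion misplaced in the exception list explains the text at least as well, because a hold followed by a deadline is the shape of a stopping rule. The objection stands, but both readings lead to the same correction.

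**The DLT parallels are weak.** Four of the seven come from a Phase 1 list that serves another purpose, in a phase already completed. That is fair. The case rests mainly on Section 4.4.2 itself.

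**Day 14 is not a scheduled ECOG visit.** The example needs an unscheduled assessment, and a corrected rule that kept Day 14 without adding one would be hard to apply. This stands and shapes the fix.

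**The practical effect is small.** A reader might infer that the protocol allows infusion at ECOG 3 or more. It does not: the bracketed hold bars it. Investigators may also stop treatment or delay a dose at their discretion. This limits the size of the problem but does not restore a mandatory stop.

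**Conclusion.** The point holds as a wording defect in a safety rule, with narrow effect. As written, the unresolved decline is exempt and the resolved one is not, and no other section sets a mandatory ECOG stop. The bullet is either inverted or misplaced; the documents do not settle which.

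The consequence is a temporary hold instead of a permanent stop, or the converse for a subject who recovers in time, and only where no other reaction already ends treatment. The documents give no count of such subjects. The 7-to-1 split describes wording and does not measure harm.

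A reader might go further and infer that the primary safety results or the efficacy analyses are compromised. The documents do not support that: no endpoint or analysis-set definition uses the bullet. At most, a subject could move in or out of the SAP 8.6.2 summary of treatment-emergent events leading to permanent discontinuation.

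The conclusion assumes that the list level and the Table 10 columns are as extracted, and that the decline is treated as a drug-related grade 3 reaction. That a stop was intended is inferred from the bullet's hold-and-deadline form, the neighbouring exceptions and the grade 2 rule.

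**What to change.** Take the bullet out of the exception list and state it as its own criterion in Section 4.4.2: *A drug-related rise in ECOG performance status to 3 or more that has not returned to 2 or less by Day 14 of the following cycle requires permanent discontinuation; one that has returned by then does not by itself require it.* Keep the bracketed hold on infusions while ECOG is 3 or more. As a criterion of its own, the stop no longer depends on how the decline is graded.

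Then make the deadline observable, in one of two ways:

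- add an ECOG check on Day 14 for subjects on hold; or
- tie the deadline to the next scheduled ECOG assessment. In 3-week cycles this adds 8 days and comes close to the grade 2 rule's end-of-cycle deadline. On the 6- and 12-week schedules it could mean a long wait, so the Day 14 check is the better choice there.

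The cost is a short amendment to Section 4.4.2 and, under the first option, one extra assessment for held subjects and a line in Table 10. The clinical downside is that subjects who recover only after the deadline stay off drug.

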4.3.1 Dermatological irAEs

Rule out non-inflammatory causes. If a non-inflammatory cause is identified, treat accordingly and continue therapy per protocol (Table 3).

Confidential Page 37 of 78

Table 3: Dermatological irAE Management Algorithm

	Dermatological irAEs	
CTCAE Grade of Rash	Management	Follow-Up
Grade 1-2 Covering ≤30% body surface area	 Symptomatic therapy (e.g., antihistamines, topical corticosteroids). Continue AGEN1884 therapy per protocol. 	 If persists >1 to 2 weeks or recurs: Consider skin biopsy. Delay AGEN1884 therapy. Consider 0.5-1 mg/kg/day methylprednisolone IV or oral equivalent. Once improving, taper corticosteroids over ≥1 month; consider prophylactic antibiotics for opportunistic infections; and resume AGEN1884 therapy per protocol. If worsens: Treat as grade 3-4.
Grade 3-4 Covering >30% body surface area; life-threatening consequences	 Delay or discontinue AGEN1884 therapy per protocol. Consider skin biopsy. Dermatology consult 1-2 mg/kg/day methylprednisolone IV or IV equivalent. 	 If improves to grade 1: Taper corticosteroids over ≥1 month; add prophylactic antibiotics for opportunistic infections. Resume AGEN1884 therapy per protocol.

CTCAE: Common Terminology Criteria for Adverse Events; irAE: immune-related adverse event; IV: intravenous; kg: kilogram; mg: milligram

Confidential Page 38 of 78

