4.3.2 Gastrointestinal irAEs

Rule out non-inflammatory causes. If non-inflammatory cause is identified, treat accordingly and continue therapy. Opiates/narcotics may mask symptoms of perforation. Infliximab should not be used in cases of perforation or sepsis (Table 4).

Table 4: Gastrointestinal irAEs Management Algorithm

Gastrointestinal irAEs							
CTCAE Grade of Diarrhea/Colitis	Management	Follow-Up					
Grade 1 Diarrhea: <4 stools/day over baseline. Colitis: asymptomatic.	 Continue AGEN1884 therapy per protocol. Symptomatic treatment. 	 Close monitoring for worsening symptoms. Educate subject to report worsening immediately. Consider symptomatic treatment including hydration, electrolyte replacement, dietary changes (e.g., American Dietetic Association colitis diet), and loperamide. If worsens: Treat as grade 2 or 3-4. 					
Grade 2 Diarrhea: 4-6 stools per day over baseline; IV fluids indicated <24 h; not interfering with activities of daily living (ADL). Colitis: abdominal pain; blood in stool.	 Delay AGEN1884 therapy per protocol. Symptomatic treatment. 	 If improves to grade 1: Resume AGEN1884 therapy per protocol. If persists >5 to 7 days or recurs: 0.5-1 mg/kg/day methylprednisolone or equivalent. When symptoms improve to grade 1, taper corticosteroids over ≥1 month; consider prophylactic antibiotics for opportunistic infections; resume AGEN1884 therapy per protocol. If worsens or persists >3 to 5 days with oral corticosteroids: Treat as grade 3-4. 					
Grade 3-4 Diarrhea (grade 3): ≥7 stools per day over baseline; incontinence; IV fluids ≥24 h; interfering with ADL. Colitis (grade 3): severe abdominal pain, medical intervention indicated, peritoneal signs. Grade 4: life-threatening, perforation	 Discontinue AGEN1884 therapy per protocol. 1-2 mg/kg/day methylprednisolone IV or equivalent. Add prophylactic antibiotics for opportunistic infections. Consider lower endoscopy. 	 If improves: Continue corticosteroids until grade 1, then taper over ≥1 month. If persists >3 to 5 days, or recurs after improvement: Add infliximab 5 mg/kg (if no contraindication). Note: Infliximab should not be used in cases of perforation or sepsis. 					

ADL: activities of daily living; CTCAE: Common Terminology Criteria for Adverse Events; h: hour; irAE: immune-related adverse event; IV: intravenous; kg: kilogram; mg: milligram.

Confidential Page 39 of 78

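### For a distinct second episode of grade 2 rash or diarrhea/colitis, Section 4.4.2 stops AGEN1884 permanently while Tables 3 and 4 resume it; the rules for a recent-onset grade 2 rash also disagree

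*Protocol*

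**What the plan says.** Protocol Section 4.4.2 applies to every grade 2 adverse drug reaction (ADR) and contains three rules that matter here.

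- Hold: "If a grade 2 ADR does not resolve to grade ≤1 by the last day of the current cycle, infusions should not be administered" in the next cycle.
- Time limit: "If, at the end of the following cycle, the event has not resolved to grade 1, the subject should permanently discontinue treatment with AGEN1884".
- Second occurrence: "Upon the second occurrence of the same grade 2 ADR (except for hormone insufficiencies that can be managed by replacement therapy"; the consequence is permanent discontinuation. Replaceable hormone insufficiency is the only exception.

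Table 4 (Section 4.3.2), in its grade 2 row for diarrhea and colitis, delays treatment. It then says "If persists >5 to 7 days or recurs: 0.5-1 mg/kg/day methylprednisolone or equivalent", followed by "When symptoms improve to grade 1, taper corticosteroids over ≥1 month; consider prophylactic antibiotics for opportunistic infections; resume AGEN1884 therapy per protocol".

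Table 3 (Section 4.3.1) puts grade 1 and grade 2 rash in one row. The initial action is "Continue AGEN1884 therapy per protocol". The follow-up column opens a second branch, "If persists >1 to 2 weeks or recurs", under which treatment is delayed and a corticosteroid considered. That branch ends "Once improving, taper corticosteroids over ≥1 month; consider prophylactic antibiotics for opportunistic infections; and resume AGEN1884 therapy per protocol".

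Section 4.1.2 lists the triggers for delaying a dose. It leaves skin events out of its grade 2 trigger and gives them their own trigger at grade 3, with a catch-all for the investigator's discretion.

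Section 4.3 describes the tables as there to assist investigators. The only event type that Section 4.4.2 sends expressly to a table is infusion and hypersensitivity reactions, to Table 2.

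**The concern.** An immune-related event is defined in Section 5.8.6.1.2 as associated with drug exposure, so a grade 2 immune-related rash or colitis is also a grade 2 ADR under Section 4.4.2. Both sets of instructions therefore apply to the same patient on the same day.

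At a distinct second episode, one site can follow the table and re-dose after steroids while another follows Section 4.4.2 and stops for good. The first site would be re-exposing a patient to a CTLA-4 blocker after a recurrence that the protocol elsewhere treats as a reason to end treatment. For a recent-onset grade 2 rash, one site doses and another withholds.

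Safety and tolerability are a primary objective. SAP Section 8.6.1 summarizes exposure and dose intensity over the first four cycles. Section 8.6.2 summarizes events that ended treatment, and the share of events leading to a hold or a stop within the rash, diarrhea and colitis clusters. Those summaries would mix two management rules.

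**Working it through.** The plan states no figure for this point. The check is a comparison of the texts, followed by an illustration with the SAP's own dose-intensity formula.

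**Texts side by side**

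| Case | Section 4.4.2 | Tables |
|---|---|---|
| Grade 2 diarrhea/colitis resolves; a distinct second grade 2 episode follows | Permanent stop | Table 4: steroid, taper once at grade 1, resume |
| Grade 2 rash resolves; a distinct second grade 2 episode follows | Permanent stop | Table 3: delay, consider steroid, taper once improving, resume |
| First grade 2 rash, recent onset, still grade 2 at cycle end | Withhold the next infusion | Table 3: continue |
| Restarting after a held first grade 2 rash | Grade 1 or lower; permanent stop if grade 1 is not reached by the end of the next cycle | Table 3: improving is enough; no grade, no time limit |

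For the third case, the next dose of a 21-day cycle falls on Day 22. A rash that began on Day 15 or later (one-week limit: 22 − 7 = 15), or on Day 8 or later (two-week limit: 22 − 14 = 8), has not passed Table 3's persistence limit. It is also outside the listed triggers of Section 4.1.2, although the investigator may still choose to delay.

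For a first episode of grade 2 diarrhea, Table 4 restarts at grade 1, which fits Section 4.4.2. Table 4 conflicts only at the second episode.

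**Illustration of dose intensity**

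Inputs: 1 mg/kg (Phase 2 dose) and 3-week cycles for the first four cycles (Protocol 4.1.1). SAP 8.6.1 divides the dose given in the first four cycles by the actual time those cycles took. After a permanent stop before Cycle 4 for a reason other than progression or death, it counts each remaining cycle as 3 weeks with no dose. Assumptions: constant weight, full doses, and a 3 to 6 week delay for the hold and taper under Table 4. The last is not in the documents; Section 4.4.2 allows a restart once prednisone or its equivalent is at 10 mg/day or below.

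Nominal: 4 mg/kg ÷ 12 weeks = 0.333 mg/kg/week.

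Second diarrhea episode (resolves in Cycle 1, returns in Cycle 2):

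- Section 4.4.2: 2 ÷ 12 = 0.167, and 0.167 ÷ 0.333 = 50%.
- Table 4, 3-week delay: 4 ÷ (12 + 3) = 0.267, or 80%.
- Table 4, 6-week delay: 4 ÷ (12 + 6) = 0.222, or 67%.

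Recent-onset rash (begins 5 days before the Cycle 2 dose, resolves during Cycle 2 within Table 3's limit):

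- Table 3 read alone: 4 ÷ 12 = 0.333, or 100%.
- Section 4.4.2, withheld dose skipped: 3 ÷ 12 = 0.250, or 75%.
- Section 4.4.2, withheld dose made up: 4 ÷ 15 = 0.267, or 80%.

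Percentages are against the nominal 12-week schedule, because the SAP divides the planned dose by actual duration too. A rash that is improving but still grade 2 is left out, because Table 3 sets no restart date.

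**The case against.** The best reply is that the texts can be reconciled. Section 4.4.2 claims every grade 2 ADR, names one exception and makes one referral to a table, which implies that rash and diarrhea stay under it. The tables only assist, and their continue and resume instructions carry the words *per protocol*. On this reading the tables treat the toxicity, and Section 4.4.2 decides whether dosing may go on. *Recurs* is also undefined; if it means symptoms returning within one episode, the second-occurrence rule is not engaged.

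Much of this stands as a guide to probable intent. It does not settle the matter. *Per protocol* names no section and is attached to most dosing actions in the tables, and neither table confines *recurs* to a flare within one episode. The reading also does less for rash: a site that follows *per protocol* to Section 4.1.2 finds grade 2 skin events outside the listed triggers. That exemption sides with Table 3 and may be deliberate. Since Section 4.4.2 looks at the last day of the cycle, just before the next dose, applying its hold would leave the exemption with almost no effect.

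A reader might infer that Section 4.4.2 clashes with all the immune-related event tables. The check shows conflict only for Tables 3 and 4 at grade 2; it offers nothing for Tables 5 to 9 or for the grade 3-4 rows. A reader might also infer that the pre-dose instruction under Table 10, which cites Section 4.1.2 alone, would cause skin or fatigue holds to be missed. That instruction sits in the laboratory footnote, where a site would not look for those holds.

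**Conclusion.** The point holds. For a distinct second grade 2 episode of rash or diarrhea/colitis, Section 4.4.2 and Tables 3 and 4 give opposite instructions, and the protocol only implies which prevails. For a first, recent-onset grade 2 rash, Table 3 and the grade 3 skin threshold in Section 4.1.2 allow a dose that Section 4.4.2 withholds, and the restart conditions differ. Which rule should govern that second case is a clinical choice for the sponsor.

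The size is illustrative: 50% against 67% to 80% of nominal dose intensity for the diarrhea case, and 75% to 80% against 100% for the rash case, on the assumptions above and with the tables read on their own. It would be tempting to conclude that the safety or exposure analyses are invalid. The documents do not support that: the analyses are descriptive, the sample size is not inferential, no endpoint or analysis set changes, and the number of subjects affected is unknown. This should be fixed because it concerns re-dosing after an immune-related event and is cheap to remove.

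**What to change.** 1. **Second episode.** Add to Section 4.4.2 that its second-occurrence stop for grade 2 ADRs takes precedence over the resume paths of Tables 3 and 4. At grade 2, qualify the recurrence branches of both tables: *resume only if Section 4.4.2 does not require permanent discontinuation*. The hormone-replacement exception stays as it is.
2. **Unresolved first grade 2 rash.** State one rule and apply it in Section 4.1.2, Section 4.4.2 and Table 3. The conservative default is the Section 4.4.2 hold, with grade 1 or lower needed to re-dose. If the sponsor intends the grade 2 skin exemption in Section 4.1.2, write that exception into Section 4.4.2 instead.
3. **Optional.** Add a cross-reference to Section 4.4.2 in the laboratory footnote of Table 10.

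The cost is an amendment with written IRB/IEC approval before implementation (Protocol 7.1), and some more held doses or discontinuations at sites that had followed the tables. No extra visits, data or patients are needed.
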